## DATA MANAGEMENT

**25.0 Data Collection\***

6.

1. *Provide a general description of the types or categories of data that will be collected during the study (e.g., lab test results, procedure outcomes, length of stay, questionnaires, surveys). Details on identifiable data and sensitive data will be described below:*

- Survey data through REDCap
- For those receiving Clinical Care there will be data collection for feasibility of the mobile unit for the following: Biological Sex of Patient, Age of Patient, Participation in Pregnancy test, STI testing for gonorrhea/chlamydia (urine), and STI testing for HIV and Syphilis (blood). Results for the following: pregnancy test, STI test results for gonorrhea/chlamydia/HIV/syphilis (urine and blood). Record of if birth control was received and which type. Record of Condoms taken. Record if referral to Children's Mercy Hospital Adolescent or Teen Clinic was given. All services are optional for teens. All information collected will be de-identified.

2. *Describe the source of the data and how that data will be obtained.*

- All data will be collected directly from participants by entry into redcap via ipad, phone call, text (Twilio), or email.

**3. Sensitive Data:** If collecting or accessing sensitive data which may pose legal, economic, or reputational harm, please specify here.

N/A

**4. Identifiable Data:** To minimize risks, only the minimum necessary identifiable data should be accessed and/or recorded. Indicate below which identifiable data elements will be accessed only versus which data elements will be recorded, i.e., written down for the purposes of this research study.

Names, phone number, and email addresses will be recorded for the purposes of the 2-, 4- and 6-month follow-up phone calls. We will also record phone numbers to send text messages to engage peer leaders. Date of birth will be recorded to assess the age of intervention trial participants. Zip codes will be recorded to identify if we are serving economically, or disadvantage youth based on their location.

a) Name/Initials	 Accessed only	 Recorded
b) All elements of date (except year) directly related to an individual (e.g. date of birth, admission date, discharge date, date of death)	 Accessed only	 Recorded
c) Medical record number	 Accessed only	 Recorded
d) Account number	 Accessed only	 Recorded
e) Health plan identification number	 Accessed only	 Recorded
f) Social Security Number	 Accessed only	 Recorded
g) Device identifiers and serial number	 Accessed only	 Recorded
h) Certificate/License number	 Accessed only	 Recorded
i) Telephone number	 Accessed only	 Recorded
j) Fax number	 Accessed only	 Recorded
k) Email addresses	 Accessed only	 Recorded
l) Web addresses (URLs); Internet IP addresses	 Accessed only	 Recorded
m) Street address, city, county, precinct, zip code or equivalent geographical codes	 Accessed only	 Recorded
n) Full face photographic images and any comparable images	 Accessed only	 Recorded
o) Biometric identifiers, including finger and voice print	 Accessed only	 Recorded
p) Vehicle identifiers and serial numbers, including license plate number	 Accessed only	 Recorded

q) Any other unique identifying number, characteristic or code that may help identify individual participants including their initials (e.g. student or employee ID number)	 Accessed only	 Recorded
r) Elements of date, including year, for persons 90 years or older	 Accessed only	 Recorded
s) Other:	 Accessed only	 Recorded

## 26.0 Adverse Events and Unanticipated Problems\*

*Intervention Trial Adolescent Participants:* In the unlikely occurrence of an adverse event or unanticipated problem, we will follow established practices for adolescents engaged in minimal risk research. It is possible that some of the intervention content may make some participants feel uncomfortable. We will clearly announce multiple times throughout the intervention duration that participation is voluntary, and adolescents may skip parts if they prefer. We have trained staff who are skilled in discussing sensitive topics like sexual health and mental health. While unlikely, someone may share information about a serious health risk to themselves or others (I.e., thoughts of hurting oneself). Our team has experience with these serious conditions and will work with community partner leaders and the parent or guardian to establish a safe care plan that may include referral to the CM emergency department for urgent evaluation.

7.

1. **Monitoring:** Describe the process for monitoring participants and data to identify adverse events and other unanticipated problems.

*Intervention Trial Participants:* Study staff will review study data every month for any adverse events.

2. **Reporting:** *Confirm Policy 5.11 Reportable Events of the CM Research Program Policies and Procedures will be followed in regards to reporting adverse events and other unanticipated problems to the CM IRB. If deviating from, or expanding upon this policy, explain why the approved policy would not suffice for this study and the rationale for deviating/expanding*

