#### RESEARCH ACTIVITIES:

#### INTERVENTION TRIAL PARTICIPANTS:

All adolescents will have access to THO+ activities and materials shared by the peer leaders.

All adolescents will be asked to complete an eligibility screening survey and baseline survey online or in-person. They will complete short surveys at 2, 4 and 6 months via Twilio text, call, or email.

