## **Intervention Trial Participants:**

For adolescents, we will review a study information sheet in-person or online (*titled Study Information Letter for Intervention Participants*). This info sheet will be available for the participant to keep. We will use a teach-back method to ensure participant understanding and ensure that the participant has the opportunity to ask questions before agreeing to participate.

**20.3 Documentation of Permission/Consent/Consent at 18:** *If selected “Written” options above, explain how informed permission will be documented. Describe:*

- *Whether CM Research Policy “10.04 Obtaining Permission/ Assent/ Consent” and “Research Documentation in the Electronic Health Record” will be followed. If not, describe whether and how permission of the parent(s)/LAR will be documented in writing.*
- *Whether e-Consent will be used to document permission (non-FDA regulated studies only).*

N/A

**20.4 Identification of participants turning 18:** *Explain the process for tracking participants to ensure that consent is obtained to continue participation once they turn 18 years of age.*

**INTERVENTION TRIAL PARTICIPANTS:** We will build a REDCap alter to indicate to study staff on the Event Daysurvey (optional) and on the *Survey Measures Interventional Trial Participants* follow-up surveys whether the adolescent has turned 18 since the baseline survey according to their date of birth. If yes, we will proceed with adult consent processes and record having done so in the REDCap survey. If the participant attends a mobile unit event and has turned 18, they will be re-consented in-person at the event. If they have turned 18 by the follow-up surveys, they will be re-consented over the phone.

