Missing data: We plan to minimize missing data by engaging our CAB to pretest survey measures to achieve brevity and clarity. Our electronic data collection tool (REDCap) can be set to require participant responses before advancing. In order to identify potential problems promptly, we will run a REDCap report every second week to review the degree of missingness for each variable. Any variable missing $>5\%$ will be reviewed to determine probable causes and a plan will be developed to address the issue(s). During analysis, we will determine both the extent of missingness and whether data are missing at random (MAR). If the data are missing for $<20\%$ of responses, we will rely on list-wise deletion. If $\geq 20\%$ is missing we will utilize multiple imputation techniques. Specifically, we will determine if data are MAR by partitioning the data into two groups (those with and without missing data) and examining the distributions across variables of interest and employ appropriate imputation techniques.

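### The only stated review of study data for adverse events is monthly, so a self-harm disclosure in a survey completed without staff contact could wait up to about a month to be read

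*Protocol*

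**What the plan says.** **Anticipated event and response.** Protocol section 26.0 states: "While unlikely, someone may share information about a serious health risk to themselves or others (I.e., thoughts of hurting oneself". The team would then work with community partner leaders and the parent or guardian on a "safe care plan that may include referral to the CM emergency department for urgent evaluation".

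**Detection.** Under Monitoring in the same section, where the template asks for the process that identifies adverse events, the answer for intervention trial participants is one sentence: "Study staff will review study data every month for any adverse events".

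**How data arrive.** Section 25.0 states: "All data will be collected directly from participants by entry into redcap via ipad, phone call, text (Twilio), or email". For enrolment, the Research Activities part of the Study Design says: "All adolescents will be asked to complete an eligibility screening survey and baseline survey online or in-person". Section 11.0 allows the 2-, 4- and 6-month surveys by phone, text or email. Section 21.3 lets adolescents who enrol virtually read the information sheet alone and agree in REDCap. Section 9.0 says the surveys contain open-ended as well as closed questions, and section 14.0 says they ask about mental and sexual health.

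**Other checks on the data.** SAP, Missing data: "we will run a REDCap report every second week to review the degree of missingness for each variable". Protocol section 20.4: "We will build a REDCap alter to indicate to study staff" that a participant has turned 18. Section 14.0 provides a phone call-back when sensitive information arrives by unsecure two-way message. Section 30.0 marks safety monitoring as not applicable because the study is minimal risk.

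**The concern.** Section 26.0 describes a response that may be urgent, but the response cannot start until someone knows of the disclosure. When staff are on the phone or in the room, they know at once. When a teenager completes a survey alone, the only content review the documents state is monthly. The participants include minors aged 14 to 17 under a requested waiver of parental permission, so a parent may not know that the survey was taken.

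Participant safety is at stake, not an estimate or a test. The study already plans REDCap tools that work faster than monthly, but the documents assign them to age and missingness. Followed as written, the plan looks for a blank field sooner than it looks at what a completed field says.

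**Working it through.** The plan has no calculated figure to reproduce. The check asks which routes leave an answer unread at entry, whether any other provision reads it sooner, and how long the wait could be.

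**Step 1: which routes are unattended.**

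| Route | Source | Staff aware at entry? |
|---|---|---|
| In-person survey or event | Study Design | Yes, if the disclosure is spoken |
| Follow-up by phone | Section 11.0 | Yes |
| Two-way text message | Section 14.0 | In part: call-back, no time limit |
| Online baseline | Study Design; section 21.3 | Not stated |
| Follow-up by text or email | Sections 11.0, 25.0 | Not stated |

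**Step 2: whether another provision reads the content sooner.**

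- The SAP's two-weekly report counts missing values. A completed answer passes it unread.
- The section 20.4 alert depends on date of birth.
- The section 14.0 call-back is there to move information to a secure platform. It does not mention survey answers stored in REDCap.
- Section 30.0 adds nothing.

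None of these is a content review of REDCap answers.

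**Step 3: the wait under monthly review.** Let T be the interval between reviews. *Monthly* is taken as T = 28 to 31 days. Two assumptions are needed: entries arrive evenly over the interval, and nobody reads them between reviews. The wait W is then uniform on (0, T), so:

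- mean = T/2
- maximum = T
- P(W > d) = 1 − d/T

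| Quantity | T = 28 | T = 31 |
|---|---|---|
| Mean wait | 28/2 = 14 days | 31/2 = 15.5 days |
| Maximum wait | 28 days | 31 days |
| P(W > 7 days) | 1 − 7/28 = 75% | 1 − 7/31 = 77% |
| P(W > 14 days) | 1 − 14/28 = 50% | 1 − 14/31 = 55% |
| P(W > 21 days) | 1 − 21/28 = 25% | 1 − 21/31 = 32% |

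**Step 4: would the two-weekly schedule be enough?** With T = 14, the mean wait is 14/2 = 7 days and the maximum 14 days. Adding safety fields to that report would halve the wait but still leave up to two weeks.

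**Step 5: volume.** With up to 250 adolescents, one baseline and three follow-up surveys each, there are at most 250 × 4 = 1,000 such surveys over the whole study. The documents do not say how many would be self-completed.

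**The case against.** The strongest reply is that section 26.0 describes two processes. The disclosure wording follows directly on a statement about trained staff who discuss sensitive topics. The monthly line answers a separate template prompt. A routine data review can sit beside an immediate response to what staff hear. This stands for live contact. It does not cover an answer typed when no staff member is there, for which the monthly line is all the protocol offers.

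Follow-ups may also be mostly live. Sections 20.1 and 25.0 call them phone calls, section 20.4 has re-consent at follow-up done by phone, and section 8.0 describes the text as an appointment reminder. This narrows the gap but does not close it, because the Study Design and sections 11.0 and 25.0 still permit text and email, and the baseline may be online.

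The survey instruments are not among the documents, and the open-ended examples in section 9.0 ask about feasibility, not mood. Whether a direct self-harm item exists, or already carries a flag, is unknown. Section 26.0 also relies on established practices that it does not set out. These points limit how likely the problem is. An open-ended field is still enough for a disclosure to be possible, which is all the protocol itself claims.

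A reader might infer three stronger things that the documents do not support:

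- **That every disclosure waits for the monthly review.** Spoken disclosures do not, and sensitive two-way texts have their own call-back, though an untimed one.
- **That section 26.0 contradicts section 20.4 or the SAP.** An age flag and a missingness report serve other purposes. The tension lies within section 26.0.
- **That entries are known to sit unread between reviews.** The documents are silent on this.

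**Conclusion.** The concern holds for self-completed surveys: the online baseline and any follow-up done by text or email. For these, the plan followed as written allows a disclosure in an open-ended answer to wait up to about 31 days, with a mean of about 15. Both figures assume even arrival and no reading between reviews. If staff in practice read entries sooner, the wait is shorter and the protocol need only say so.

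The protocol itself calls such a disclosure unlikely, so the expected number is small, and the documents give no rate from which to estimate it. The point is still more than a missing detail, because a stated schedule does not fit the urgency that the same section foresees. No estimate, test or sample size is affected. The monthly review is stated only for intervention trial participants; section 26.0 gives no interval for event day participants.

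**What to change.** Reconcile the monthly review in section 26.0 with that section's own urgent-evaluation wording. Section 26.0 should provide that self-completed answers able to carry a safety disclosure, including free text, are flagged to study staff at entry. The REDCap alert function already planned in section 20.4 can do this. The monthly review stays as a backstop. The study team sets the timing for reading flagged entries and states it, and the clinical response remains as the protocol defines it. Adding these fields to the SAP's two-weekly report would not be enough alone, since it leaves up to 14 days.

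The cost is REDCap configuration, a short addition to section 26.0 and a small amount of existing staff time. A free-text alert fires on harmless comments too, and someone must read each one. With at most 1,000 baseline and follow-up surveys over the study, and only some of them self-completed, that load is modest.

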## 27.0 Data Analysis\*

8.

1. *Describe the data analysis plan, including any statistical procedures or power analysis.*

*Describe how the sample size for the study was determined (e.g. formal sample size calculation, convenience sampling). To minimize the risks associated with a possible breach of confidentiality, appropriate sample size calculations limit the amount of patient data being recorded to the amount necessary to answer the research question.*

Quantitative data: We will conduct descriptive analysis with inferential and graphical exploratory analytic techniques, presenting mean, median, and interquartile range [continuous variables] and frequency and percentage [categorical variables]. We will examine outliers and/or influential points, perform bivariate analyses to assess relationships, and summarize group data. We will use SAS 9.4 (SAS Institute Inc., Cary, NC, USA); the significance level will be 0.05. For our primary outcome, we calculate the proportion in each arm with any health care utilization at 6 months. We use logistic regression to assess intervention effect on utilization and explore differences in other outcomes. Models will include covariates to adjust for variables (e.g., sex, age) that may increase precision. We will explore heterogeneity of effects with stepwise addition on interaction terms to examine moderation by sex, age, or engagement. If >20% of data is missing, we will use complete cases or imputation, based on missingness pattern.

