## **Study Design**

### **Study Design: Open Clinical Trial**

#### PROGRAM ACTIVITIES:

*AccessKCTeen 2.0* is an outreach program that deploys Children Mercy's Staff and Mobile Unit into the community to increase access to SRH and MH care and resources. *AccessKCTeen 2.0* will focus on education, peer leaders, and community partnership. All events are optional for adolescents to attend.

*Mobile Unit Demonstration Events:* The CM mobile unit will go to community sites where members of the CM *AccessKCTeen* team will do the following: provide education on telemedicine, SRH, and MH, answer questions on accessing care, SRH, and MH, and help adolescents get registered for telemedicine or other care at CM.

*Mobile Unit Clinical Care Events:* The CM mobile unit go to community sites where members of the CM *AccessKCTeen* team will provide direct clinical services, such as testing for infections or pregnancy, birth control counseling, and birth control.

Any teen can attend these events. If they choose to attend an event, they must enroll in our Event Day Survey, to receive clinical medications (e.g., emergency contraception, birth control pills, birth control patch) or testing as this is a requirement for pharmacy documentation. This survey will ask for contact information which is required to track clinical medications and provide testing results.

**THO+:** Teens as part of a friend network, where peer leaders in each network work with health professionals and trusted adults to connect adolescents in their networks to health information and sources for care.

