## 9.0 Surveys and Psychometric Testing:

- *Describe any surveys or psychometric testing that will be conducted as part of the study. Address whether the instruments used have been previously validated.*
  - INTERVENTION TRIAL PARTICIPANTS: Surveys include:
    - (*Titled Survey Measures Interventional Trial Participants*) Eligibility Screen, contact form, baseline survey
    - (*titled Survey Measures Intervention Trail Participant*): 2, 4, 6 follow-up
    - Event Day Survey Measures (optional).
    - Surveys will include both closed-ended and open-ended questions (see table below). When possible, we will use previously validated measures.
    - Peer Leaders in the THO+ arm will complete check-ins by text message, on-line or in-person.
  - ADOLESCENT EVENT PARTICIPANTS: Survey (*titled Event Day Survey Measures*) at the event day survey (optional).

Feasibility constructs (Bowen et al.) and sample measures		
Construct	Source	Sample Measure*
Acceptability - How do stakeholders react?	Adolescent	Satisfaction**; Recommend to friends**;
Demand - To what extent is the intervention likely to be used?	Adolescent	Likelihood to use again**; proportion of friends who would use
Implementation - To what extent can the intervention be implemented as planned?	Adolescent	Engagement**; "What toolkit ideas worked well/not so good?"
	Study Record #	Fidelity to peer leader training, engagement, attendance
Practicality - What factors make intervention delivery challenging or facilitate delivery?	Adolescent	Ease of talking with friends about health**
	Study Record #	Field notes

Integration - To what extent can intervention be integrated within community?	Adolescent	Frequency of network health information exchange** "What was it like to learn about SRH/MH health at community partner?"
Expansion - To what extent can model be expanded?	Adolescent	Openness to vaccine information using intervention**
Limited efficacy - Does the intervention show promise?	Adolescent, Study/Medical Record #	Health care utilization (yes/no; also where accessed, what type);  new patient registration (yes/no); care-seeking intention**

\*Appendix has complete list of closed- and open-ended items; \*\*Likert responses range from 1 ("strongly disagree") to 5 ("strongly agree"); #Additional assessments: proportion enrolled, attendance for study activities

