## 28.0 Data and Specimen Management\*

9.

1. **Data Management:** *Describe how data will be handled, including:*

- *What information will be included with the data?*

- *Intervention Trial Participants:* Survey information included as data will be questions from our eligibility screen, baseline survey, Event Day Survey Measures(optional) and 2-, 4-, and 6-month follow-up. We will ask adolescents about their health behaviors as well as some demographics to describe the group (age, gender identity, race). Attendance at study-related events, training, and group sessions will be included as data.
- *Event day Participants:* Survey information included as data will be questions from our eligibility screen, and Event Day Survey Measures (optional). For those receiving Clinical Care

the information included as data: Participation in Pregnancy test, STI testing for gonorrhea/chlamydia (urine), and STI testing for HIV and Syphilis (blood). Results for the following: pregnancy test, STI test results for gonorrhea/chlamydia/HIV/syphilis (urine and blood). Record of if birth control was received and which type. Record if referral to Children's Mercy Hospital Adolescent or Teen Clinic was given. All services are optional to teens.

- *How the data will be collected and stored. (e.g., REDCap, Excel, paper forms)*
  - All data will be directly accessible and stored securely via REDCap at CMKC.
- *How long will the data be stored?*
  - Contact information for teens that would like to participate in future research will be kept for 5 years and then destroyed. For teens that do not want to participate in future research, we will destroy contact information as soon as the study is completed. De-identified data will be stored in accordance with CMRI guidelines and will be deleted once IRB project is closed
- *Who will have access to the data?*
  - CM study team, students from the University of Kansas Medical Center (KUMC) and University of Missouri – Kansas City (UMKC) will have access. A reliance will be obtained from both institutions.
- *Who is responsible for receipt or transmission of the data?*
  - Trained CM research team members and students from the University of Kansas Medical Center (KUMC) and University of Missouri – Kansas City (UMKC)
- *Methods for transferring data.*
  - All data that is shared will be de-identified using a secure data transfer system.

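### Protocol 27.0 lists engagement as a moderator, but it is measured after enrolment over the outcome window; with one arm, only an engagement–utilization association remains, and it can be non-null even if THO+ has no effect.

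*Protocol*

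**What the plan says.** Protocol 27.0 states the primary analysis as "we calculate the proportion in each arm with any health care utilization at 6 months", with logistic regression for the intervention effect. It then says "We will explore heterogeneity of effects", by "stepwise addition on interaction terms to examine moderation by sex, age, or engagement". It gives no definition, source or time window for engagement.

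The feasibility table in Protocol 9.0 places engagement under implementation, from two sources. One is an adolescent-reported item on a 1-to-5 agreement scale. The other is the study record: "Fidelity to peer leader training, engagement, attendance". Protocol 28.0 adds: "Attendance at study-related events, training, and group sessions will be included as data". Protocol 11.0 sets the intervention and follow-up period at six months.

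On overlap with the outcome, Study Design (Program Activities) says that staff at clinical care events "will provide direct clinical services, such as testing for infections or pregnancy, birth control counseling, and birth control". The Table of Events gives intervention participants an optional mobile unit event that may include medicine and testing. The outcome measure in 9.0 is "Health care utilization (yes/no; also where accessed, what type", with no stated exclusion of care received at the unit.

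On design, the Revision History records removal of the THO arm at revision 3, and Research Activities gives all adolescents access to THO+. The SAP contains no regression, interaction or moderation analysis. It evaluates the feasibility constructs, implementation among them, with descriptive statistics.

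**The concern.** A moderator should be a characteristic that the intervention cannot change, fixed before the outcome can occur. Engagement meets neither condition, and three features make it awkward here:

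- It accrues over the six months in which utilization is counted, so the order of cause and effect is not fixed.
- One visit to a clinical care event may count both as engagement and as utilization.
- Teens who already want care may both engage more and use more care, whatever THO+ does.

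The stake is interpretation. In a one-group study, a result that more engaged teens used more care is easily read as a dose-response effect of THO+. Presented as moderation of an intervention effect, it would carry a causal meaning that the design cannot support.

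**Working it through.** The documents give no expected rate, effect size or power, so there is no figure of the plan's own to reproduce. The check asks what an engagement analysis could show if THO+ had no effect.

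**1. What can be estimated.** Take a model with an intercept, arm, engagement and arm × engagement. When every participant is in THO+, the arm column equals the intercept and the product column equals engagement. The design matrix has rank 2 out of 4. Neither the arm term nor the interaction can be estimated; only the engagement term is left.

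**2. Overlap alone.** Suppose engagement is scored as attendance at a clinical care event. Let p0 be the proportion using care elsewhere, the same in attenders and others. Let u be the share of attenders who take a service that counts as utilization. Then

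- attenders: p1 = 1 − (1 − p0)(1 − u)
- odds ratio = [p1/(1 − p1)] / [p0/(1 − p0)]

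Worked case: p0 = 0.3 and u = 0.7 give p1 = 1 − 0.7 × 0.3 = 0.79, so OR = (0.79/0.21)/(0.3/0.7) = 8.78.

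| p0 (assumed) | u = 0 | u = 0.25 | u = 0.5 | u = 0.7 |
|---|---|---|---|---|
| 0.3 | 1.0 | 2.11 | 4.33 | 8.78 |
| 0.5 | 1.0 | 1.67 | 3.00 | 5.67 |
| 0.7 | 1.0 | 1.48 | 2.43 | 4.33 |

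If every attender takes a counted service (u = 1), all attenders are users and the odds ratio is infinite.

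Next is the chance of p < 0.05 (two-sided) with N = 250, the enrolment ceiling, over p0 = 0.3–0.7 and attendance of 20% or 40% (assumed). It is about 5% at u = 0, 17–80% at u = 0.25, and 58–100% at u = 0.5. With 200 analysed (an assumed 20% loss), the last two ranges become 14–71% and 48–100%.

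**3. Shared care-seeking alone.** Here no visit counts twice and engagement has no effect, but an unmeasured tendency raises both engagement and utilization. In 2,000 simulated trials of 250, with log-odds of 0, 0.5 and 1.0 per standard deviation of that tendency, the odds ratio was about 1.0, 1.24 and 2.02. The proportions of trials with p < 0.05 were 4.6%, 14% and 77%. This route does not require engagement to be scored as attendance.

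**The case against.** **The planned interaction cannot be run.** True, and the odds ratios above are therefore main effects of engagement, not a measure of bias in a moderation estimate. But the only version of the analysis that can be run with one arm is the association itself. Correcting the leftover two-arm wording would not by itself remove engagement from the list.

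**The SAP already treats engagement descriptively.** Largely right, and the fix follows it. However, the SAP is dated 5 September 2023 and the protocol's latest revision 15 December 2023. The SAP does not withdraw the moderation analysis, and it allows bivariate tests at p < 0.05 that could include this pair of variables.

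**Engagement need not mean attendance.** A reader might infer that the analysis is bound to show a strong association. The documents do not support that. Section 9.0 lists attendance separately from engagement in the study record and also has a rating-scale item. Program Activities describes demonstration events as education and registration help, although section 17.0 allows emergency contraception to be handed out there. With low service uptake, or with the rating-scale item and little shared care-seeking, the association could be weak or absent.

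**Care at the unit is real care.** This stands in part. Visits prompted by peer leaders would be the intended mechanism. But any teen may attend events, so the data cannot separate prompted visits from visits that would have happened anyway.

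**Early dropouts cannot accumulate engagement.** A reader might add this as a further source of association. The SAP largely answers it by excluding participants lost at 6 months from denominators for hypothesis testing. It could matter only if their outcomes were imputed.

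**Conclusion.** The point holds in a limited form. Engagement is undefined in 27.0, is measured after enrolment over the outcome window, and may overlap with the outcome, so it should not be listed as a moderator beside sex and age. An engagement–utilization association can appear with no THO+ effect.

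Its size depends on rates the documents do not give and on how engagement is scored. If it is clinical-event attendance, the odds ratio is about 1.5–2.1 at 25% uptake with care elsewhere at 30–70%. It is 3.0–8.8 at 50–70% uptake with care elsewhere at 30–50%; if care elsewhere is 70%, the value at 50% uptake falls to 2.4. Without overlap or shared care-seeking it is 1.0. These figures assume that use of care elsewhere is unrelated to attendance and that attendance is not itself caused by THO+. The survey appendix is not among the documents, so the exact wording of the items could not be checked.

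The analysis is exploratory, and the primary proportion with any utilization at 6 months is not affected.

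**What to change.** - Delete engagement from the moderator list in Protocol 27.0, and reconcile that paragraph with the single-arm design and the SAP.
- Report engagement descriptively as an implementation measure, as the SAP already does for feasibility constructs. State which source and time window define it.
- State whether care at the mobile unit counts as utilization.
- If an association with utilization is reported, give it with a confidence interval and call it an association, not moderation or effect. Use the item on where care was accessed to show mobile unit care and other care separately.
- Optionally, relate engagement up to month 2 to utilization outside the unit reported at months 4 and 6. This needs dated engagement records and survey questions limited to the period since the previous survey. It removes the overlap but not confounding by care-seeking.

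The cost is a wording change, with no new data for the main correction. The optional analysis sets aside engagement after month 2 and care delivered at the unit, so it loses some precision. How much cannot be worked out, because the documents do not say when events fall relative to enrolment.
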